7.2.1.6 SFU[6W], SFU[12W], SFU[24W], SFU[36W], SFU[48W], and SFU[60W]

These visits are applicable for all patients unless locally CT-verified PD occurs. In case of PD this visit should be considered the End-of-Study Visit.

If SFU[60W] is scheduled ≥ 76 weeks since Screening this visit should be considered the End-of-Study Visit, *Section 7.2.1.7*.

TIME WINDOWS:

SFU[6W]: 6 weeks (± 7 days) after Sun-Start Visit
SFU[12W]: 12 weeks (± 7 days) after Sun-Start Visit
SFU[24W]: 24 weeks (± 7 days) after Sun-Start Visit
SFU[36W]: 36 weeks (± 7 days) after Sun-Start Visit
SFU[48W]: 48 weeks (± 7 days) after Sun-Start Visit
SFU[60W]: 60 weeks (± 7 days) after Sun-Start Visit

NB: The CT/MRI scans do not have to be done the very same day as the corresponding study visits. However, each CT/MRI scan has to be done within the specified time window for the corresponding visit.

ACTIVITIES AND ASSESSMENTS:

The same activities and assessments will be done at these visits as was done on Sun-Start Visit except for auto- and alloimmunization, *Section 7.2.1.5*. In addition to dispense of sunitinib, the site personnel will collect unused and empty sunitinib packages (distributed at the previous visit) from the patient for drug accountability, *Section 9.1.4*.

7.2.1.7 End of Study Visit

This visit is applicable for all patients.

TIME WINDOW:

78 ± 2 weeks after Screening

NB: The CT/MRI scan does not have to be done the very same day as the study visit. However, it has to be done within the above specified time window.

ACTIVITIES AND ASSESSMENTS:

The same activities and assessments will be done at this visit as was done on SFU[6W] to SFU[60W] Visits, *Section 7.2.1.6*. No dispense of sunitinib will be done.

7.2.1.8 Safety Evaluation 30 Days after Last Dose of Investigational Medicinal Product

The safety evaluation, i.e. collection of SAEs, as described in *Section 11.2* is applicable for all patients who have received any IMP.

ACTIVITIES AND ASSESSMENTS:

- SAEs, *Section 11.2*

7.2.1.9 Extra Visits

Extra Visits are applicable for all patients if any symptoms need follow-up between planned visits.

TIMING:

The patient will be scheduled for a visit as soon as possible.

ACTIVITIES AND ASSESSMENTS:

- Concomitant Medication, *Section 10.4.4*
- Physical Examination, *Section 10.5.3*
- Vital Signs, *Section 10.5.4*

- Laboratory Safety Blood Assessments: Hematology and Clinical Chemistry. If the Extra Visit is scheduled after the Sun-Start Visit the assessments will also include GFR based on Creat, Gluc, TSH, and Thyroxine [free T4], *Section 10.5.5*
- Laboratory Safety Urine Assessments, *Section 10.5.5*
- ECOG performance status, *Section 10.2.3.1*
- AEs, *Section 11.2*
- Additional laboratory tests and other assessments as applicable to the discretion of the Investigator

7.2.1.10 Post-Study Survival Information

This measure is applicable for all patients.

- Survival data, *Section 11.3*

7.2.2 Study Flow Charts

Detailed instructions on vital signs, AE collection, and blood sampling in connection to vaccination are shown in *Table 3*.

Table 2 Study Flow Chart

Visit	Screening Day 1	Vacc1 Intuvax + sunitinib Day 2-28 sunitinib only N/A	Vacc2 Intuvax + sunitinib Day 16-42 sunitinib only N/A	Nephrectomy Intuvax + sunitinib Day 19-63 sunitinib only Day 63 at the latest	Sun-Start 5 to 8 weeks after Nephrectomy	SFU[6W] 6w ±7d after Sun-Start SFU[12W] 12w ±7d after Sun-Start SFU[24W] 24w ±7d after Sun-Start	SFU[36W] 36w ±7d after Sun-Start SFU[48W] 48w ±7d after Sun-Start SFU[60W] ^o 60w ±7d after Sun-Start	End-of-Study 78w ±2w after Screening	Safety Evaluation Collection of SAEs up to 30 days after last dose of IMP	Extra visit When needed
Informed consent	X	X ^e								
Demography	X									
Medical and Surgical History	X									
CT/MRI scan ^l	X ^m				X ^t	X ^t		X ^t		
Prior and/or Concomitant Medication	X	X	X	X ^a	X	X		X		X
Physical Examination	X	X	X		X	X		X		X
Vital Signs ^b	X	X ^c	X ^c		X	X		X		X
ECG	X									
Hematology and Clin. Chem.	X	X ^d	X ^d	X ^{a,d}	X ^u	X		X		X
GFR based on Creat, Gluc, TSH, and Thyroxine (free T4)	X				X	X		X		X ⁿ
PT-INR	X	X ^d	X ^d	X ^{a,d}						
APTT	X	X ^d	X ^d	X ^{a,d}						
Pregnancy	X ^e	X ^e	X ^e							
Urinalyses	X	X ^d	X ^d	X ^a	X ^u	X		X		X
HIV/HBV/HCV and HLA	X									

Cont. Table 2 Study Flow Chart

Visit	Screening Day 1	Vacc1 Intuvax + sunitinib Day 2-28 sunitinib only N/A	Vacc2 Intuvax + sunitinib Day 16-42 sunitinib only N/A	Nephrectomy Intuvax + sunitinib Day 19-63 sunitinib only Day 63 at the latest	Sun-Start 5 to 8 weeks after Neph ^l	SFU[6W] 6w ±7d after Sun-Start SFU[12W] 12w ±7d after Sun-Start SFU[24W] 24w ±7d after Sun-Start	SFU[36W] 36w ±7d after Sun-Start SFU[48W] 48w ±7d after Sun-Start SFU[60W] ^o 60w ±7d after Sun-Start	End-of-Study 78w ±2w after Screening	Safety Evaluation Collection of SAEs up to 30 days after last dose of IMP	Extra visit When needed
Auto- and Alloimmunization		X ^f			X ^f					
ECOG performance	X	X ^d	X ^d		X	X	X	X		X
Karnofsky performance	X									
■	X			X ^a	X	X	X	X		
Inclusion/Exclusion criteria	X ^g									
Randomization	X ^g									
Confirmatory diagnostic biopsy	X ^p									
Nephrectomy				X						
Biopsies (tumor x2, adjacent normal tissue)				X						
Administration of Intuvax ^q		X ^c	X ^c							
Sunitinib dispense & return ^h					X ⁱ	X	X	X ⁱ		
AEs	X	X ^c	X ^c	X	X	X	X	X ^k	X ^v	X
Diagnosis Confirmation ^f				X						

a Assessment to be completed before nephrectomy and may be done the day before nephrectomy for logistical reasons

Locally analyzed Creatinine for patients included in the study before 28 August 2017 (if performed as part of clinical routine) to be recorded in eCRF

b Height only at Screening. Weight at all visits except for Vacc1 and Vacc2 Visits.

c See specific flow chart, *Table 3*, for detailed instructions on pre- and post-vaccination assessments.

d Physical examination, ECOG performance, and samples for safety lab and urinalyses may be taken the day before vaccination for logistical reasons

Locally analyzed results for Hb, WBC, platelets, PT-INR, and APTT need to be available before vaccination

Locally analyzed results for Hb, WBC, and clinical chemistry might need to be available prior to nephrectomy

- Analysis of coagulation status at Nephrectomy is not necessary provided the patient is not on anticoagulant treatment. For patients on anticoagulants local sampling practice applies.
- e Pregnancy test in blood at Screening, and in either blood or urine at Vacc1 and Vacc2 Visits. The pregnancy test result is needed prior to each vaccination.
 - f Samples for auto- and alloimmunization analyses will be collected prior to vaccination at Vacc1 Visit. Sampling at Sun-Start Visit only applicable for patients randomized to Intuvax.
 - g To be done when the results from all assessments made are available. Telephone contact with patient to inform about treatment and timing of next study visit.
 - h The prescribed dose to be in accordance with the SmPC/USPI including any dose adjustments.
 - i Return of sunitinib not applicable at Sun-Start Visit and Distribution not applicable at End-of-Study Visit. Standard of Care applies after End-of-Study.
 - j Start of sunitinib administration will be dependent on wound healing. The time window for initiation is five (5) to eight (8) weeks after Nephrectomy.
 - k Post-study collection of survival data.
 - l If CT cannot be used for some reason, MRI is acceptable. The same modality has to be used at all visits.
 - m CT scan to be done within 3 weeks before Screening unless a CT scan has been done in clinical routine within 6 weeks before Screening. Brain imaging (preferably by contrast-enhanced) MRI or CT to be done within 3 weeks before Screening Visit unless a CT scan has been performed in clinical routine within 6 weeks prior to Screening Visit
 - n To be done if Extra Visit is scheduled after Sun-Start Visit
 - o If SFU[60W] is scheduled ≥ 76 weeks since Screening this visit should be considered the End-of-Study Visit
 - p Confirmatory diagnostic biopsy in accordance with local routines prior to Vacc1 Visit, if required by local regulations and laws
 - q Absolute fasting for four (4) h prior to Intuvax administration applies
 - r Routine histology/Primary diagnosis is assessed locally
 - s Extra consent for vaccination for patients randomized to the vaccine arm, to be taken after randomization if required by local regulations
 - t The CT scan does not have to be done the very same day as the corresponding study visit. However, each CT scan has to be done within the specified time window for the corresponding visit
 - u The laboratory safety blood and urine assessments do not have to be done the very same day as the study visit. However, it has to be done within 3 days prior to the visit.
 - v SAEs only to be recorded and reported, see *Section 11.2*

Table 3 Detailed Instructions on Assessments in Connection with Vaccination

Assessment	Pre-vaccination	Vaccination	Post-vaccination					
	> 2 h	0 h	15 min (±5 min)	30 min (±10 min)	60 min (±10 min)	2 h (±10 min)	3 h (±10 min)	4 h (±20 min)
Intuvax injection		X						
BP	X		X	X	X	X	X	X
HR	X		X	X	X	X	X	X
Body temperature	X			X	X	X	X	X
AEs	X		X	X	X	X	X	X

7.3 Discussion of Study Design, Including the Choice of Control Groups

Intuvax is developed as an immune primer for cancer treatment that preferably should be combined with a drug that acts in synergy with Intuvax by inhibiting tumor-induced immunosuppression. In this study, Intuvax is given in combination with sunitinib, which like several other TKIs is known to inhibit myeloid-derived suppressor cells [25]. Based on current ESMO and NCCN guidelines [26, 27, 28] today's standard of care both in US and in the majority of the European countries involves initiation of systemic treatment with a TKI (including sunitinib or pazopanib) approximately 6 weeks post nephrectomy for all patients regardless of prognosis, i.e. poor (high risk) or intermediate. It is anticipated that all patients will benefit more from vaccination with Intuvax the sooner TKI treatment is initiated after performed nephrectomy.

Sunitinib alone was chosen as the active control for the study based on its documented positive impact on tumor response, PFS and OS in patients with mRCC. As discussed in *Section 5.2* it is hypothesized that sunitinib might contribute to an increased Intuvax efficacy.

7.4 Study Period

Expected timelines in the study:

Start of inclusion: Q2 2015

Planned last patient last study visit or last patient's safety evaluation (up to 30 days after the last patient's last dose of an IMP), whichever occurs later: Q3 2019

7.5 End of Study

The end of study is defined as the last patient last visit (LPLV) or the last patient's safety evaluation (up to 30 days after the last patient's last dose of an IMP), whichever occurs later.

8 SELECTION OF STUDY POPULATION

8.1 Number of Patients

The estimated number of patients to be randomized in the study is around 90. The patients will be randomized in a 2:1 (vaccination:control) ratio. Stratification will be done at randomization for intermediate- and high-risk patients, *Section 3.2*, and *Section 9.2*.

The choice of sample size is discussed in *Section 12.2*.

The study will be performed at approximately 25 sites in EU and approximately 5 sites in US. Competitive recruitment will apply.

8.2 Inclusion Criteria

The patients have to meet all of the following criteria to be eligible to enter the study:

- 1) Newly (<6 months) diagnosed RCC (histological/cytological verification is optional) with at least one (1) CT-verified metastasis ≥ 10 mm for which complete metastasectomy is not planned. US patients must have verified clear-cell tumor histology
- 2) Planned resection of primary tumor
- 3) Primary tumor diameter ≥ 40 mm
- 4) Candidate for first-line therapy with Sunitinib initiated five (5) to eight (8) weeks after nephrectomy
- 5) Female or male ≥ 18 years of age
- 6) Willing and able to provide informed consent
- 7) Adequate hematological parameters, i.e.:
 - B-Leukocyte count $\geq 4.5 \times 10^9/L$
 - B-Platelet count $\geq 150 \times 10^9/L$
 - B-Hemoglobin (Hb ≥ 90 g/L)
- 8) Serum-creatinine and serum-bilirubin $\leq 1.5 \times$ ULN. Serum-ALAT and serum-ASAT $\leq 2.5 \times$ ULN (or ≤ 5 in case of liver metastases)
- 9) Female who has been post-menopausal for more than one (1) year or female of childbearing potential agreeing to use a highly efficient method of contraception (i.e. a method with less than 1% failure rate [e.g. sterilization, hormone implants, hormone injections, some intrauterine devices, or vasectomized partner or combined birth control pills]) from Screening until 90 days after last dose of Intuvax and/or until completed sunitinib treatment whichever occurs later. Female of childbearing potential must have a negative blood pregnancy test at Screening, and if randomized to vaccination a negative blood or urine pregnancy test within one (1) day before each dose of Intuvax) and must not be lactating.

or

Male agreeing to use condoms from Screening until 90 days after last dose of Intuvax and/or until completed sunitinib treatment whichever occurs later, or male having a female partner who is using a highly efficient method of contraception as described above.

8.3 Exclusion Criteria

Patients meeting any of the following criteria will not be permitted to enter the study:

- 1) Life expectancy less than 4 months
- 2) CNS metastasis that is symptomatic or progressing or untreated or that required current therapy (e.g. evidence of new or enlarging CNS metastasis or new neurological symptoms attributable to CNS metastases)
- 3) Active autoimmune disease which requires treatment with systemic immunosuppressive agents, e.g. inflammatory bowel disease, multiple sclerosis, sarcoidosis, psoriasis, autoimmune hemolytic anemia, rheumatoid arthritis, SLE, vasculitis, Sjögren's syndrome, scleroderma, autoimmune hepatitis, and other rheumatological diseases
- 4) Treatment with per oral systemic corticosteroids exceeding 10 mg/day within 7 days before Screening until Nephrectomy (inhaled, intranasal and local steroids acceptable irrespective of dose)
- 5) Known cardiomyopathy and/or clinically significant abnormal ECG findings at Screening disqualifying the patient from nephrectomy and subsequent sunitinib treatment
- 6) Karnofsky performance status <70%, *Section 3.2*
For patients in **France** Karnofsky performance status ≤70%, *Section 3.2*
- 7) National Cancer Institute (NCI) Common Terminology Criteria for Adverse Events (CTCAE) Grade 3 hemorrhage within 28 days before Screening
- 8) Pre-existing thyroid abnormality with thyroid function that cannot be maintained in the normal range with medication
- 9) Clinically significant gastrointestinal abnormalities
- 10) Uncontrolled hypertension or uncontrolled diabetes mellitus
- 11) Pulmonary embolism within 12 months prior to Screening
- 12) Prior history of invasive cancer within 5 years before Screening, except for adequately treated *in situ* carcinomas or non-melanoma skin cancer
- 13) Ongoing infection that requires parenteral treatment with antibiotics
- 14) Active or latent virus disease (HIV, HBV and HCV)
- 15) ECOG performance status >2 after optimization of analgesics, *Section 3.2*
- 16) Abnormal or clinically significant coagulation parameters at the discretion of the investigator, i.e.:
 - Prothrombin Time - International Normalized Ratio (PT-INR)
 - Activated Partial Thromboplastin Time (APTT)Patients being treated with anticoagulants are excluded if the coagulation parameters are outside the therapeutic intervals as described in the SmPC/USPI for the administered treatment
- 17) Known major adverse reaction/event in connection with previously made vaccination (e.g. asthma, anaphylaxis or other serious reaction)
- 18) Known hypersensitivity or allergy to sunitinib or to chemically related products or likely to be exacerbated by any component of the study products

- 19) Prior systemic antitumor therapy within 28 days before Screening Visit. However, local radiation therapy to any area except for the abdominal/retroperitoneal area including the kidney tumor is allowed
- 20) Exposure to other investigational products within 28 days prior to Screening Visit
- 21) Patients on anticoagulants for whom temporarily stop and start, supported by low molecular weight heparin (or other anticoagulation therapy at the discretion of the Investigator and/or per local standard of care) during vaccination and nephrectomy, is not an option
- 22) History of alcohol or substance abuse
- 23) Any reason that, in the opinion of the Investigator, contraindicates that the patient participates in the study

8.4 Restrictions

Intuvax: Treatment requires absolute fasting for a period of 4 hours prior to vaccination.

Sunitinib: Restrictions for treatment as in the SmPC/USPI for Sutent® (sunitinib), e.g. avoid concomitant administration of potent CYP3A4 inducers or inhibitors.

Nephrectomy: Same restrictions apply as in clinical routine.

8.5 Removal of Patients from Therapy or Assessment

Patients are free to discontinue their participation in the study at any time. Withdrawal from the study will not affect or prejudice the patient's further care or treatment. Patients may be withdrawn from study treatment and assessments at any time, if deemed necessary by the Investigator.

Patients who discontinue treatment with Intuvax and/or sunitinib for safety reasons (including DLT, see *Section 11.5*) or due to concomitant medication (*Section 9.6*) will not necessarily be considered withdrawn from the study unless there are other reasons for withdrawal. They should return for all following visits and assessments until PD.

Examples of reasons for withdrawal of patients from this study are:

- Progressive disease on sunitinib treatment
- Screening failure
- The decision of a patient to withdraw from the study (i.e. if the patient withdraws informed consent)
- Administration of concomitant medication prohibited by this protocol, *Section 9.6*
- Pregnancy
- Patient is lost to follow-up
- RCC diagnosis is not confirmed by histological findings from the biopsy collected at nephrectomy or, if applicable, from confirmatory pre-study treatment diagnostic biopsy

The reason and date the patient is withdrawn from the study and subsequent planned replacement therapy will be documented in the electronic case report form (eCRF).

All patients that have received IMP must have safety evaluations for 30 days after the last dose of IMP, *Section 11.2*.

If a patient is withdrawn from further assessments, the Investigator should attempt to complete all discharge procedures, i.e. End-of Study Visit. All AEs should be followed up according to *Section 11.2*.

If a patient is withdrawn from the study, all data collected until the time of withdrawal will be used in the analyses.

Survival data (including post-study survival data if applicable) will be collected and analyzed for all patients withdrawn from the study, *Section 11.3*.

Patients randomized to Intuvax who withdraw from the study before administration of the first dose of Intuvax will be considered screening failures. Patients randomized to sunitinib alone who withdraw from the study before any assessments made at the first visit following Screening will be considered screening failures.

Only patients considered screening failures will be replaced.

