7.2.1.4 Nephrectomy Visit

This visit is applicable for all patients.

TIME WINDOWS:

At least 3 days after Vacc2 Visit and within 63 days from Screening Visit for patients randomized to Intuvax followed by sunitinib.

Within 63 days from Screening Visit for patients randomized to sunitinib only.

ACTIVITIES AND ASSESSMENTS:

Prior to Nephrectomy (may be done the day before vaccination for logistical reasons)

- Concomitant Medication, *Section 10.4.4*
- Laboratory Safety Blood Assessments: All patients: Hematology and Clinical Chemistry, for patients on anticoagulants: also PT-INR, and APTT, *Section 10.5.5*

- Laboratory Safety Urine Assessments, *Section 10.5.5*
- █████, *Section 10.2.3.2*
- AEs, *Section 11.2*

Nephrectomy and post Nephrectomy assessments

- Nephrectomy, *Section 9.1.1*
- Biopsies for central assessments of infiltrating CD8+ T-cells and immunohistology, *Section 10.2.2.4* and *Section 10.2.3.3*.
- AEs, *Section 11.2*
- Confirmation of mRCC diagnosis, *Section 10.4.2*

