11.2 Reporting of Adverse Events

Adverse event reporting and data management will be performed according to the following relevant guidelines:

- Directive 2001/20/EC (European Clinical Trial Directive),
- CPMP/ICH/E2A/377/95 (Clinical Safety Data Management: Definition and Standards for Expedited Reporting),
- CPMP/ICH/135/95 (GCP),
- 21 CFR 312.32 (FDA).

All study patients will be carefully monitored for the occurrence of AEs during the study period from Screening Visit to the completion of the End-of-Study Visit. SAEs will be collected until completion of the End-of-Study Visit or up to 30 days after last dose of IMP administered in the study, whichever occurs later.

All patients who received IMP who withdraw less than 1 month after IMP administration must have safety evaluations, defined as recording and reporting of any SAE, for 30 days after the last dose of Intuvax or Sunitinib. The Investigator will collect AEs with a non-leading question such as “have you experienced any new health problems or worsening of existing conditions” as well as reporting events directly observed or spontaneously volunteered by patients.

Clearly related signs, symptoms and abnormal diagnostic procedure results should be grouped together and reported as a single diagnosis or syndrome whenever possible.

All AEs including but not limited to events reported by the patient, or reported in answer to an open question by the Investigator or member of this team, which fall into any of the above definitions must be recorded as an AE in the eCRF and should include the following information:

- Brief description of the event (diagnosis)
- Start date (and time, if relevant)
- Stop date (and time, if relevant) (or resolution)
- Severity
- Action taken regarding IMP
- Opinion on causality
- Seriousness
- Outcome

The general term “Progressive Disease” (PD) should not be used when reporting an AE. Instead, all symptoms, laboratory findings etc. including those that could be a reflection of PD should always be reported.

Severity describes the intensity of an event, and will be assessed using the NCI CTCAE version 4.0 [2]. The CTCAE displays Grades 1 through 5 with unique clinical descriptions of severity for each AE based on this general guideline. The term Grade refers to the severity of the AE. The following grades are used:

Grade 1 (Mild)

Asymptomatic or mild symptoms OR clinical or diagnostic observations only OR intervention not indicated.

Grade 2 (Moderate)

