Safety Evaluation 30 Days after Last Dose of Investigational Medicinal Product

All patients who have received IMP will have a safety evaluation, i.e., recording of SAEs for 30 days after last dose of IMP. The safety evaluation will be performed either as (i) a visit to

the clinic by the patient, (ii) a phone call to the patient by site personnel, or, if contact with the patient is not possible for any reason, (iii) as a review of the patient's medical records. All SAEs detected during the safety evaluation will be recorded in the eCRF and reported to [REDACTED] Drug Safety in accordance with the procedure presented in *Section 11.3*.

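### After withdrawal, new SAEs are collected by time from the last IMP dose, not from nephrectomy, so patients who leave before sunitinib get 0 further days in the control arm and 0 to 27 in the Intuvax arm

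*Protocol*

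**What the plan says.** **The 30-day rule.** Protocol 8.5 requires that "All patients that have received IMP must have safety evaluations for 30 days after the last dose of IMP". Protocol 7.2.1.8 says that the evaluation "is applicable for all patients who have received any IMP". Protocol 11.2 names the two products that start the clock for patients who withdraw: "for 30 days after the last dose of Intuvax or Sunitinib". The Synopsis and 7.1 set the same condition. Nephrectomy does not start a window anywhere.

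**The general SAE period.** Protocol 11.2, matched by 10.5.2, says "SAEs will be collected until completion of the End-of-Study Visit or up to 30 days after last dose of IMP administered in the study", taking the later of the two. On withdrawal, 8.5 asks the investigator to try to complete the End-of-Study Visit. For a withdrawn patient with no IMP clock running, that visit closes the collection of new SAEs.

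**Timing.** In the Intuvax arm, nephrectomy takes place "At least 3 days after Vacc2 Visit and within 63 days from Screening Visit for patients randomized to Intuvax followed by sunitinib" (7.2.1.4). In the control arm the first IMP is sunitinib, five to eight weeks after surgery (7.2.1.5).

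**Ways out in between.** Reasons for withdrawal in 8.5 include the patient's own decision and that "RCC diagnosis is not confirmed by histological findings from the biopsy collected at nephrectomy".

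**What does not depend on IMP.** AEs ongoing at withdrawal are followed (11.2), and survival data are collected for all withdrawn patients (8.5).

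**Use of the data.** Safety in vaccinated and non-vaccinated patients is a secondary objective (Protocol 6.2). The safety set in SAP 5 keeps controls who never received an IMP, and SAP 6.3.10 summarises AEs by treatment group.

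**The concern.** Both arms have the same operation, but at the time of surgery only one arm has an IMP clock running. Take two patients who leave on the same post-operative day, each with a new serious complication a week later. If the Intuvax patient is still within 30 days of the last dose, that event is recorded. The control patient's event is not. The control patient stays in the safety set, so the missing event counts as no event.

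The control arm is the trial's only concurrent reference for what surgery itself causes. Under-recording there makes Intuvax look worse. The route out may also differ by arm. Where local law requires a confirmatory biopsy before vaccination, Protocol 9.2 books it for patients randomised to Intuvax. A non-RCC diagnosis could then surface before surgery in that arm, but only at nephrectomy in controls.

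**Working it through.** The plan gives no figure for this point, so the check is day arithmetic on its own windows.

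**Inputs**
- Window: 30 days from the last IMP dose (8.5, 11.2).
- *g* = days from Vacc2 to nephrectomy, minimum 3 (7.2.1.4). From Table 2 (Vacc2 Day 16-42, nephrectomy by Day 63) the maximum is 63 − 16 = 47. With Vacc1 on Day 2 and the shortest dose interval of 14 − 3 = 11 days, Vacc2 falls on Day 13 and the maximum is 63 − 13 = 50.
- *w* = days from nephrectomy to the exit visit.
- Interval before sunitinib: 35 to 56 days after surgery (7.2.1.5).

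**Further days of new-SAE collection after exit, before sunitinib**
- Control: 0, because no IMP has been given.
- Intuvax, both doses given: max(0, 30 − *g* − *w*).

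| *g* (days) | *w* = 0 | *w* = 7 | *w* = 14 | *w* = 21 |
|---|---|---|---|---|
| 3 | 27 | 20 | 13 | 6 |
| 7 | 23 | 16 | 9 | 2 |
| 14 | 16 | 9 | 2 | 0 |
| 21 | 9 | 2 | 0 | 0 |
| 30 or more | 0 | 0 | 0 | 0 |

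The entries are also the differences between arms, since control is always 0. The difference runs from 0 to 27 days and is gone once *g* + *w* reaches 30. Even at *g* = 3, an Intuvax patient who leaves on post-operative day 27 or later is treated exactly like a control, although the interval before sunitinib lasts 35 days or more.

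**Which gap is likely?** The documents do not say. Protocol 9.1.1 expects Intuvax to delay surgery by 14 to 20 days, which equals (14 − 3) + 3 to (14 + 3) + 3. My inference is that surgery was expected close to the 3-day minimum, which leaves up to 27 days. In the phase I study (Protocol 5.1) surgery came two weeks after the second dose, which leaves up to 30 − 14 = 16.

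**From leavers to the arm.** With about 90 patients randomised 2:1, the control arm has about 90 × 1/3 = 30 patients, so each control leaver is about 1/30 = 3% of the arm. The number leaving in this interval is not given, nor is the timing of SAEs, so the calculation stops there.

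**The rule proposed under the fix.** With a floor of 30 days after nephrectomy, control cover after exit is max(0, 30 − *w*). Intuvax cover is the larger of max(0, 30 − *w*) and max(0, 30 − *g* − *w*). Since *g* is at least 3, the first always governs and the arms are equal.

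**The case against.** The case against giving this much weight is strong in several respects.

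- **Most post-operative SAEs are collected alike.** While a patient is on study, SAEs are recorded in both arms whether or not an IMP was given. Patients who stop treatment for safety reasons are not necessarily withdrawn and are asked to keep attending (8.5). Events ongoing at exit, and deaths, are followed in both arms. A reader might infer from the 30-day rule that post-operative SAEs in general are collected unequally by arm, or that any Intuvax patient who leaves before sunitinib is followed. The documents support neither.
- **The size cannot be pinned down.** A reader might assume, say, that 10 to 20% of controls leave in the first post-operative week and derive a percentage of SAEs missed for the arm. No document supports such a rate. Withdrawal for unconfirmed histology must also wait for a pathology result, so an exit on the day of surgery is unlikely for that reason. SAP 6.3.6 does say that some intermediate-risk patients under protocol versions before 4.0 never started sunitinib. They cannot all be counted as affected: only exits within the first 27 post-operative days, or fewer with a longer gap, could be.
- **No perioperative comparison is planned.** The AE tables in SAP Appendix 1 include none for the period after nephrectomy; those bounded by visits end at first vaccination or at surgery. The summaries are descriptive and the trial is exploratory.
- **The direction is not the dangerous one.** Under-recording in controls counts against Intuvax and does not hide its harm.
- **The rule is consistent.** It is stated the same way throughout, so this is a design choice and not a contradiction.

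All of this limits the point, but none of it removes it. Following ongoing AEs does not capture a new event, and survival data capture only the fact and date of death. For new SAEs after an early exit, ascertainment still depends on the arm.

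**Conclusion.** The point holds in a narrow form. For patients who withdraw after nephrectomy and before sunitinib, new SAEs after the exit visit are collected for 0 further days in the control arm and for 0 to 27 in the Intuvax arm. This affects only new SAEs, apart from the fact and date of death, in patients leaving within 30 days of the last Intuvax dose or at the equivalent point in controls.

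The day counts rest only on the protocol's windows and assume that both Intuvax doses were given. The effect on the by-arm SAE tables cannot be quantified without the number of such withdrawals. It is probably small, and its direction is against Intuvax. Because the gap is built into the rule and cheap to close, it is worth correcting, but it does not call the wider safety comparison into question.

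**What to change.** **Rule.** In Protocol 7.2.1.8, 8.5, 10.5.2 and 11.2, collect SAEs in every randomised patient who undergoes nephrectomy, in both arms and whether or not an IMP was given, to the latest of the End-of-Study Visit, 30 days after the last IMP dose and 30 days after nephrectomy. Use the visit, telephone or record-review route that 11.2 already provides.

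**Patients who have already left.** The new wording may reach few or no future patients. The planned last visit is Q3 2019 (7.4) and End-of-Study is at least 76 weeks after Screening, so on plan the last Screening was by mid-April 2018. Nephrectomy within 63 days takes that to mid-June 2018, and sunitinib within eight weeks to mid-August 2018. The SAP cites a protocol version dated February 2019, which I take to be the one supplied. The practical step is therefore one record review before database lock, to post-operative day 30, of every patient in either arm who left between nephrectomy and sunitinib, where consent permits. It must cover both arms: reviewing controls alone would take them to day 30 while Intuvax leavers stop at day 27, 23, 16 or 9 for gaps of 3, 7, 14 or 21 days, which reverses the imbalance.

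**Reporting.** Give the number of such patients by arm, and state the limitation where review is not possible, for example after withdrawal of consent.

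**Cost.** A short text change and a little extra site work for a few patients.
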